## Criteria for Early Discontinuation

### Criteria for Early Discontinuation

#### Early Discontinuation During the Inpatient Lead-In Phase:

Patients who demonstrate worsening psychiatric symptoms, such as the emergence of severe depression, anxiety or significant suicide risk, will be removed from further participation and provided the appropriate level of care in the inpatient unit, followed by referral to appropriate treatment. Patients who develop signs and symptoms of severe alcohol withdrawal (e.g. delirium, requiring > 16 mg Ativan over 24 hours, CIWA-Ar>15 at any assessment) will be transferred to a medical unit for detoxification in coordination with the Milstein Hospital Medicine service, as per usual 5S unit protocol, and then removed from study participation. The usual aftercare following discharge for medical detoxification at Milstein Hospital includes referrals to appropriate treatment. Patients who sign out of the hospital against medical advice during the inpatient lead-in phase will be removed from further participation and provided referrals for appropriate treatment.

Early Discontinuation During 10-Day or 30-day DIS Treatment:

Certain patients may be required to discontinue DIS and will thus be removed from study participation, but will be allowed to continue receiving treatment in the STARS clinic if they so choose. These include patients who repeatedly drink heavily while taking DIS; any female participant with a positive pregnancy test; and patients who develop intolerable side effects from DIS (e.g. severe sedation). For these patients, DIS will be discontinued and they will be offered to continue treatment at STARS for the remainder of the study period. This treatment will include weekly meetings with a psychiatrist who will administer appropriate behavioral (e.g. CBT and Motivational Interviewing) and/or pharmacological treatments (e.g. naltrexone, acamprosate, topiramate) for Alcohol Use Disorder.

Patients who demonstrate clinical worsening that requires a higher level of care than can be provided at the STARS clinic will be removed from study participation and provided appropriate referrals. Clinical worsening will be determined by the judgment of the STARS psychiatrist in consultation with the PI, and will include the emergence of serious withdrawal symptoms (e.g. seizures or delirium tremens), serious medical consequences (i.e. physical symptoms requiring emergency room visits, liver failure), dangerous behaviors (e.g. physical aggression), significantly worsening depression or anxiety (increase in HAM-A or HAM-D by more than 15 points from baseline), active suicidal or homicidal ideation or behavior, or clinical deterioration indicated by a CGI-I of 6 or above on 2 consecutive sessions. The psychiatrist will make a determination of the need for a higher level of care, or to an emergency room, and will provide referrals as appropriate.

**Blood and other Biological Samples**

Please create or insert a table describing the proposed collection of blood or other biological specimens

	Time to Complete (minutes)	Screening	Inpatient admission	Pre-DIS MRI scan	10-day DIS treatment (every visit)	10-day DIS treatment (final visit)	Post -DIS MRI scan	Weekly during 30-day DIS treatment (including optional extension)	End of 30-day DIS treatment	Weekly during optional 30-day DIS treatment extension
Breath alcohol testing	1	RA	RA		RA		RA	RA		RA
Urine drug/EtG screen	1	RA		RA		RA		RA		RA
Urine pregnancy	1	RA		RA			RA			

screen									
Vital signs	1	RA	RN	RA	RA	RA	RA	RA	
Blood test	1	RA				RA			RA
EKG	10	RA							

RA=Research Assistant RN=Nurse

## Assessment Instruments

Create a table or give a brief description of the instruments that will be used for assessment

At screening, the RA will administer a 30-day Timeline Followback (TLFB) to quantify alcohol use and will include the Montreal Cognitive Assessment (MOCA) to assess cognitive functioning. The psychotherapist will administer the Mini International Neuropsychiatric Instrument (MINI) to diagnose Alcohol Use Disorder and other psychiatric disorders. The psychiatrist will administer a psychiatric evaluation; the Hamilton Depression Inventory (HAM-D); the Hamilton Anxiety Inventory (HAM-A); the Clinical Institute for Withdrawal Assessment - Revised (CIWA-Ar); the Clinical Global Impression Scale (CGI); and the Treatment Services Review (TSR).

During the inpatient admission the patients will complete the following self-report questionnaires: The Barratt Impulsiveness Scale (BIS) will assess the level of trait impulsivity. The Alcohol Dependence Scale (ADS) will assess the severity of Alcohol Use Disorder. The Obsessive Compulsive Drinking Scale (OCDS) will assess the level of alcohol incentive salience. The Readiness to Change Questionnaire (RCQ) will assess the motivation to reduce drinking. The Alcohol Abstinence Self-Efficacy Scale (AASE) will assess the level of self-regulation of alcohol-seeking motivation. The Drinker Inventory of Consequences (DrInC) will assess prior experiences with negative consequences from alcohol. The Domain Specific Risk Taking Scale (DOSPERT) will assess the level of risk aversion/preference in a variety of domains. The DIS-Risk scale will ask two questions rating the perceived likelihood and unpleasantness of the DIS-alcohol reaction.

The OCDS, RCQ, AASE will be repeated on the last day of the 10-day DIS treatment, at the STARS clinic, prior to the post-DIS MRI scanning session. The ACQ, FCQ and the DIS-Risk will be administered right before the MRI scans.

Citations for these instruments, as well as the schedule for administration, may be found in the section "Assessments".

The DIS-Risk is the only non-standard instrument. It comprises the following two items: (1) "How certain are you that drinking alcohol today would result in an unpleasant physical reaction?" (1 = "I am completely certain that I will not have any reaction"; 10 = "I am completely certain that I will have a reaction") and (2) "Assuming that this reaction will happen, how unpleasant/painful do you think it will feel?" (1 = "It won't be unpleasant at all;" 10 = "It will be the most painful feeling I have ever had").

Please attach copies, unless standard instruments are used  
Assessments.pdf

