Previous work by the PI(5) and others(6) has provided circumstantial evidence that excitatory inputs from the insula and the ventromedial prefrontal cortex (VMPFC) into the ventral striatum (VS) drive a specific “goal-directed” form of drug and alcohol seeking that is engaged when there is a high level of subjective risk. The PI has also shown that cue-induced alcohol craving can be reduced by thinking about risks of alcohol use(7). In cigarette smokers, this risk-based form of cognitive regulation of craving is mediated by negative functional connectivity between the dorsolateral prefrontal cortex (DLPFC) and the VS(8). Furthermore, effective AUD treatments consistently down-modulate cue-induced activity in the VS(9), suggesting an important role for this region in therapeutic behavior change.

Based upon this prior work, we propose that DIS treatment - specifically, the mere belief that drinking will cause the DIS-alcohol reaction - changes behavior by promoting a goal-directed mode of cue-induced alcohol seeking. In this mode, the output of the VS is governed by a balance between (1) excitatory inputs from the insula and the VMPFC that together represent the incentive value of alcohol, and (2) inhibitory inputs from the DLPFC that down-modulate VS output according to the perceived unpleasantness and likelihood of the DIS-alcohol reaction. The resulting VS output determines the magnitude of cue-induced craving during DIS treatment, and predicts the likelihood of relapse during DIS treatment.

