All patients will be given thiamine 100 mg daily, folic acid 1 mg daily and a multivitamin table daily, to address nutritional deficiencies that can accompany AUD. Additionally, patients will be provided the following as-needed medications: Benadryl (diphenhydramine) 50 mg at bedtime for insomnia; Tylenol (acetaminophen) 650 mg every 6 hours for pain and headache; Maalox (magnesium/aluminum hydroxide) 30 cc once daily for gastrointestinal distress; and Compazine (prochlorperazine) 10 mg every 6 hours for nausea.

All patients will participate in the milieu therapeutic activities (e.g. recreation groups), and will be subject to the same rules and restrictions of all other voluntary patients on the unit. Patients will also complete a number of self-report assessments, administered by the RA, on the first or second day of admission (see Assessment Instruments).

On the day of discharge, patients will undergo the pre-DIS MRI scanning session. Once this scan is complete, the patients will return to the unit, where they will receive the first dose of DIS 500 mg, followed by instruction by the inpatient psychiatrist about DIS-alcohol reaction (see below for details). Following this, they will be discharged, with a follow-up appointment to attend the STARS clinic 2 days later. Prior to discharge, patients will be given a card (attached) that instructs them on the consequences of consuming alcohol while taking DIS, a list of common products that contain alcohol and are to be avoided (e.g. cough syrups, hand sanitizers), as well as a telephone number to reach the STARS on-call MD in the event of any problems or concerns.

10-Day DIS Treatment:

The 10-day treatment period will involve supervised dosing of DIS 500 mg every other day, administered by either a physician or a nurse. Two days after discharge from the inpatient unit, patients will attend the STARS clinic for the first of 4 clinic visits that will occur every other day to facilitate observed dosing of DIS to ensure full therapeutic effects for the post-DIS MRI scan. The STARS clinic is located at [name] in midtown Manhattan.

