Upon arrival at MRI facility, participants will meet with a research assistant, who will administer all of the procedures during the fMRI scan. A physician will not be present for the MRI scans, consistent with usual MRI center policies for scans that do not involve contrast agents or medications being administered during the scans. Participants will be screened for metallic devices and implants using a metal detector (a self-report screening will have occurred prior to enrollment). The urine sample obtained at the STARS clinic will have been tested for pregnancy. Participants will be administered the Alcohol Craving Questionnaire (ACQ) to assess the current level of alcohol craving, the Food Craving Questionnaire (FCQ) to assess the current level of food craving/hunger. The scanning procedure will be reviewed and the participant will be free to ask questions prior to the scan.

During each of the scans, participants will undergo the Cue Exposure task (20 minutes). This is a previously validated passive cue-exposure task that involves showing the participants pictures of alcohol and food cues in randomized order, and then asking them to rate their desire to consume the depicted item on a 1-5 Likert scale after each cue. The Cue-Exposure task is expected to increase cravings for alcohol and food, and the analysis of brain activity will focus on how DIS treatment changes cue-induced craving and cue-induced neural activity in response to alcohol and food cues, respectively. Additionally, participants will undergo a resting fMRI scan (10 minutes) and an anatomical MRI scan (5 minutes).

Following each scan, patients will complete the DIS-Risk questionnaire to assess for the level of belief that alcohol use will lead to the DIS-alcohol reaction.

The MRI scanning procedure will take approximately 1.5 hour, including 1 hour within the scanner. Participants will be paid \$50 for the first fMRI scanning session and \$100 for the second fMRI scanning session, whether or not they complete the scanning procedures.

You can upload charts or diagrams if any  
Ativan taper schedules.pdf  
Instructions to patients taking disulfiram.pdf

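### The protocol schedules DIS-Risk, the Aim 1 mediator, both right before and after the scan in different sections; given before, it could prime the cue task, so one order should be fixed

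*Protocol*

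**What the plan says.** The protocol gives two timings for DIS-Risk around the scans.

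- **Assessment Instruments:** "The ACQ, FCQ and the DIS-Risk will be administered right before the MRI scans". The same section also lists the scale with the questionnaires completed during the inpatient admission.
- **MRI Scanning:** "Following each scan, patients will complete the DIS-Risk questionnaire". The instruments this section names for completion on arrival, before scanning, are the alcohol and food craving questionnaires (ACQ and FCQ). DIS-Risk is not among them.

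Assessment Instruments describes the content: "The DIS-Risk scale will ask two questions rating the perceived likelihood and unpleasantness of the DIS-alcohol reaction". Item 1 reads "How certain are you that drinking alcohol today would result in an unpleasant physical reaction", and item 2 asks how unpleasant or painful the reaction would feel.

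The Background section says that "cue-induced alcohol craving can be reduced by thinking about risks of alcohol use", and that in cigarette smokers this kind of regulation works through negative DLPFC-VS connectivity. Aim 1 predicts, from the pre- to the post-DIS scan, less craving, less VS activity and more negative DLPFC-VS connectivity. It makes the risk ratings at the post-DIS scan the mediator of the connectivity change. The SAP also plans a mediation analysis on the perceived reaction but does not say when the rating is taken.

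**The concern.** The two timings are not interchangeable. A rating completed just before the cue task asks the patient to picture the alcohol reaction minutes before craving and connectivity are measured. On the protocol's own rationale, that thought can move the outcomes in the direction Aim 1 predicts. A rating completed after the task cannot affect that scan.

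What is at stake is the interpretation of the pre-to-post change. If the prompt acts more strongly at the second scan, part of the change would come from the measurement procedure and be credited to disulfiram treatment. If staff follow different sections, exposure to the prompt would also vary between patients or between a patient's two scans. The mediation analysis is affected too, because neither document says whether a before-scan or an after-scan rating enters the model.

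**Working it through.** The plan states no effect size, alpha, power or SD, so there is no figure to reproduce. The check is a comparison of sections, followed by an illustration under assumptions.

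**1. Is the conflict real?** Assessment Instruments groups DIS-Risk with ACQ and FCQ before the scans. MRI Scanning names ACQ and FCQ beforehand and places DIS-Risk afterwards. Assessment Instruments points to a separate schedule of assessments that is not in the supplied text. Even if that schedule settles the order, one of the two protocol sentences is wrong.

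**2. What reaches the pre-post change?** Let d be the true treatment effect on an alcohol-cue outcome, and let p_pre and p_post be the questionnaire's effect at each scan.

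- Observed change = d + (p_post − p_pre).
- Rating before both scans: the common part cancels and only p_post − p_pre remains. A difference is plausible, because no disulfiram has been taken at the first scan, while the second follows 10 days of dosing and repeated warnings. If the prompt acts more strongly at the first scan, it dilutes the change instead.
- Rating after both scans: neither cue task has DIS-Risk immediately before it.
- Rating before one scan and after the other: nothing cancels.

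**3. Does the design remove it?** The cue-by-time contrast is (alcohol change) − (food change). The prompt concerns alcohol only. If it has no effect on food cues, p_post − p_pre passes unchanged into the contrast. The Background section states that the pilot has no control group.

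**4. What could an unequal shift do? (illustration)** Assumptions, none from the documents: paired t-test, two-sided 5%, no true effect (d = 0). Sample size from the protocol: n = 25 completers.

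- Let s = (p_post − p_pre) / SD of the within-patient change.
- Non-centrality = s × √25 = 5s, with 24 degrees of freedom.
- Chance of a significant result = P(|T| > 97.5% point of t with 24 df), where T is non-central t.

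| Assumed shift s | Non-centrality 5s | Chance of a significant change |
|---|---|---|
| 0 | 0 | 5% (nominal) |
| 0.1 | 0.5 | 7.7% |
| 0.2 | 1.0 | 16.1% |
| 0.3 | 1.5 | 30.2% |
| 0.4 | 2.0 | 48.4% |
| 0.5 | 2.5 | 67.0% |

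For scale, the same test has 80% power at about 0.58 SD. The documents do not indicate which row applies, if any.

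**5. Which order suits the mediation?** A before-scan rating precedes the outcome, as a mediator should, but may alter it. An after-scan rating leaves the outcome alone but follows it, so the cues and the patient's own craving may colour it. Each choice has a cost. The before-scan cost can fall on every Aim 1 cue outcome; the after-scan cost falls on the rating and the analyses that use it.

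**6. The word *today* in item 1.** The pre-DIS scan is on discharge day. Patients then go back to the unit, "where they will receive the first dose of DIS 500 mg". A patient who reads *today* as this moment and one who reads it as later that day could reasonably give different answers at the first session. The ambiguity concerns the pre-DIS rating; Aim 1 names the post-DIS rating as mediator.

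**The case against.** The strongest reply is that awareness of risk is the treatment mechanism under study. A difference in perceived threat between the scans is largely what Aim 1 sets out to measure, and two rating items may add little to it. The post-DIS scan follows a clinic visit that same day at which staff give disulfiram and instruct about the reaction, and patients carry a warning card. Moving the questionnaire removes neither. This stands as a limit on the likely size. It does not make the order irrelevant: the instruction belongs to the treatment, whereas a questionnaire is there to measure and should not alter what it measures.

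Three further points also stand. The Background says risk thoughts *can* reduce craving; its connectivity evidence comes from smokers; and neither statement concerns a two-item rating. Priming shared by both scans cancels. And a before-scan rating has the better temporal order for mediation, so moving it afterwards has a real cost.

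A reader might infer that the protocol plans DIS-Risk twice around each scan. The text does not support that: the arrival list under MRI Scanning omits the scale, so these read as two alternative schedules. A reader might also infer that the *today* wording invalidates the mediation analysis. It does not reach the mediator as Aim 1 defines it, and what patients know at the first session about that day's dose depends on consent content not in the supplied text.

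**Conclusion.** The protocol contradicts itself on when its named mediator is collected, and the difference could affect Aim 1. If DIS-Risk is given right before the cue task, any part of its effect that differs between scans would add to or mimic the predicted change, and neither the food-cue contrast nor a control group would remove it.

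The tempting stronger conclusion, that the questionnaire would itself produce the Aim 1 findings, is not supported. The size of any unequal priming is unknown, and its direction is not certain. The table shows only what assumed shifts would do under a simple paired test. The *today* ambiguity is minor and matters only if the pre-DIS rating or a change score is interpreted. This is an inexpensive correction that should be made. In a pilot that openly acknowledges other confounds, it is not a fatal fault.

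**What to change.** 1. Correct Assessment Instruments to match the detailed procedure under MRI Scanning: ACQ and FCQ before the scan, DIS-Risk after the cue task, in the same order at both sessions. Check the separate assessment schedule against this.
2. State in Aim 1 and the SAP that the post-DIS rating collected at that point enters the mediation analysis.
3. Acknowledge in the SAP that this rating is taken after the outcome and may be influenced by the cues, so the mediation result cannot establish temporal order.
4. If the pre-DIS rating or a change score is to be interpreted, refer item 1 to the present moment at both sessions.

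The cost is a few sentences and a wording change to one item of a study-made scale, with no added visit or procedure. The scientific cost is the weaker temporal order in item 3.

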## Research Related Delay to Treatment

Will research procedures result in a delay to treatment?

No

Treatment to be provided at the end of the study

Patients will be provided appropriate referrals for AUD treatment at the end of study.

## Clinical Treatment Alternatives

Clinical treatment alternatives

The study provides a standard, evidence-based treatment for alcohol dependence. Disulfiram is a an FDA-approved medication for Alcohol Use Disorder that has been available for over 75 years, and will be provided at no cost during the study by psychiatrists who are trained in addiction treatment. In addition to the treatment provided by the study, participants will be allowed to participate in a 12-step program such as Alcoholics Anonymous.

Participants will be informed of alternatives to participation in the proposed trial. The alternative procedures available are individual counseling by other clinicians, or more intensive treatment for heavy drinking such as inpatient or outpatient detoxification, inpatient rehabilitation, or intensive outpatient programs. Additionally, there are a number of alternative medications that may aid in relapse prevention, including naltrexone (Revia) and acamprosate (Campral). More intensive treatment will be indicated if the study treatment is not helpful in the reduction of drinking, if drinking increases substantially during the study period, or if serious psychiatric symptoms (severe depression and anxiety, suicidal ideation) emerge during the course of the study.

## Risks/Discomforts/Inconveniences

Risks that could be encountered during the study period

Screening and Consent:

During the screening and consent process, there is a risk that patients may arrive either severely intoxicated to the extent that they pose a danger to themselves or others (e.g. falls, aggression, suicidal ideation), or in alcohol withdrawal that poses a threat to their physical safety (e.g. dehydration, seizures, delirium tremens). Patients will also undergo screening EKG's, Breathalyzers, blood tests and urine tests. The blood tests will require venipuncture, which will be associated with mild discomfort and a small risk of bleeding and

---

infection.

Inpatient Lead-In Phase:

Patients will be hospitalized briefly on an inpatient unit. This will be inconvenient for some patients, especially those who are working and/or who have childcare responsibilities. The physical risks of the inpatient lead-in phase are primarily related to the risk of alcohol withdrawal syndrome that may emerge upon sudden cessation of alcohol use. All of the baseline assessments, including self-reports and structured interviews, are all non-invasive and add no special risk, although they do cover sensitive areas. The major disadvantages are the time taken to complete them, and possible breach of confidentiality. Our past experience indicates that these measures and tests are acceptable to participants.

Disulfiram Treatment:

Disulfiram is an FDA-approved medication for AUD that has been used in clinical practice for over 75 years. The most common risks are related to the DIS-alcohol reaction, which occurs when patients use alcohol while taking DIS, even in small amounts. The DIS-alcohol reaction includes flushing, throbbing in head and neck, headache, shortness of breath, nausea, vomiting, sweating, thirst, chest pain, palpitation, dyspnea, hyperventilation, tachycardia, hypotension, syncope, marked uneasiness, weakness, vertigo, blurred vision, and confusion. In severe reactions there may be respiratory depression, cardiovascular collapse, arrhythmias, myocardial infarction, acute congestive heart failure, unconsciousness, convulsions, and death. The intensity of the reaction varies with each individual, but is generally proportional to the amounts of disulfiram and alcohol ingested. The duration of the reaction varies from 30 to 60 minutes, to several hours in the more severe cases, or as long as there is alcohol in the blood.

Additional adverse effects of disulfiram are unrelated to the consumption of alcohol, i.e. they are direct effects of disulfiram. Serious adverse reactions that have been reported include optic neuritis, peripheral neuropathy, psychosis and hepatic failure. Hepatic failure is the most serious and life threatening of adverse effects, and has an incidence of between 1/10,000 and 1/30,000 patient-years of disulfiram treatment, and appears to be mediated by an idiosyncratic immune-mediated mechanism that is distinct from alcohol-induced liver injury (11). Less serious, but more common, adverse reactions include benign rash, transient fatigue, impotence, headache, tremor, mild liver function abnormalities and a metallic taste. These more common adverse effects are usually transient and improve spontaneously after 1-2 weeks, and also with dose reduction. Psychotic reactions have been noted, attributable in most cases to high dosage, combined toxicity (with metronidazole or isoniazid), or to the unmasking of underlying psychoses in patients with underlying risk factors (e.g. a prior history of schizophrenia or bipolar disorder). Additionally, rare hematologic reactions have been reported (e.g. agranulocytosis, thrombocytopenia).

In addition to specific risks related to taking disulfiram, there are general risks associated with treating AUD. For example, patients may demonstrate an escalating pattern of alcohol use that can lead to serious adverse medical, legal and interpersonal problems. These risks are presumably lower than for patients who are not seeking treatment, so they do not represent an increased risk due to study participation. Some patients may demonstrate worsening psychiatric symptoms, such as depression, anxiety and suicidal ideation, either as a result of ongoing or worsening alcohol use, or as a result cessation of alcohol use (i.e. withdrawal-related).

fMRI scanning:

---

fMRI scans pose "Minimal Risk" to participants assuming that all precautions are taken, e.g. subjects must be free of implanted metallic devices or any metal fragments/objects in the body. Participants will be screened a total of 3 times for metallic devices, implants or other contraindications to scanning (once during screen assessment, once prior to first scan, and once prior to the second scan). All female subjects will be asked to take a urine based pregnancy test that will be administered prior to the scans by a female nurse on site at the fMRI Research Center.

While there are no known risks or harmful long-term effects of being placed in a magnet of the strength used in the study (3 Tesla), it is possible that some subjects might experience minor discomfort by the confined and noisy conditions typical of an MRI scanner. All equipment is FDA approved for use in an MRI environment. Brain imaging in this study will be performed on GE 3Tesla MRI scanner dedicated to fMRI research and located in the MRI Facility at the NY SPI. All equipment is FDA approved for clinical MR scanning, commercially available. The fMRI procedure is noninvasive and involves no known incremental risk. MRI devices with a magnetic strength less than 8 Tesla and within FDA specified parameters fall in the category of non-significant risk devices for all persons over the age of one month (<http://www.fda.gov/cdrh/d861.html>).

The MRI system, using both hardware and software constraints, automatically limits the power and rates of change of magnetic fields according to FDA regulations (<http://www.fda.gov/cdrh/ode/guidance/793.html>). The specific absorption rate (SAR) will not be greater than: (1) 4 W/kg averaged over the whole body of any period of 15 minutes, (2) 3 W/kg averaged over the head for any period of 10 minutes, (3) 8 W/kg in any gram of tissues in the head or torso, (4) 12 W/kg in any gram of tissue in the extremities for any period of 5 minutes. MRI and fMRI studies that do not involve sedation may be considered minimal risk assuming the proper exclusionary precautions have been taken (e.g., metal implants).

Describe procedures for minimizing risks

Screening

The screening procedures involve evaluation by a psychiatrist, including psychiatric evaluation (including a detailed history of prior alcohol withdrawal symptoms), medical examination and physical examination. This is being done specifically to identify alcohol withdrawal, intoxication or psychiatric symptoms that pose a significant risk (e.g. suicidal or homicidal ideation). The psychiatrist will make a determination of whether the participant requires immediate referral to an emergency department. The blood samples will be collected by RA's and RN's who are trained in venipuncture.

Inpatient Lead-In Phase

The inconvenience of the inpatient admission will be minimized by having as much of the admission as possible occur over the weekend, based on patient preference. The risks of alcohol withdrawal will be minimized by careful screening by a psychiatrist to exclude participants who have a history of significant withdrawal symptoms. This will include checking the breathalyzer result and the CIWA-Ar at the screening and excluding patients with a BAL = 0 who also have a CIWA-Ar > 8. Patients with any history of severe alcohol withdrawal (e.g. seizures or delirium tremens) will be excluded regardless of the CIWA-Ar or BAL at screening.

Together, these screening procedures will minimize the number of patients requiring detoxification during the inpatient hospitalizations. However, despite these procedures, a small number of patients may require detoxification. These patients will be quickly identified using CIWA-Ar given every 4 hours on the first 24

---

hours of admission. A standard symptom-triggered detoxification protocol will be initiated at the first signs of alcohol withdrawal (CIWA-Ar >8). Avoiding Friday admissions will allow the physician on the inpatient unit to determine the effectiveness and safety of the detoxification medications administered in the first 24 hours and make appropriate adjustments and schedule a taper for the duration of the hospital admission. This physician will also be able to address whether the patient is at risk of severe withdrawal requiring a medical admission. These are all procedures that are commonly utilized on dual-diagnosis and detoxification units in clinical settings, such that study participation will not pose any added risk of withdrawal that is greater than if the patients were to undergo standard inpatient treatment for alcohol use disorder.

The self-report baseline assessments will be administered in a private area, to minimize the chance that confidentiality will be violated. Also, standard practices to preserve patient confidentiality that are employed on 5-S will be in place for this study.

